5.3 Prohibited/Cautious Medications and Therapy

Anti-cancer therapy for another active malignancy or MF including chemotherapy, immunotherapy, radiotherapy, hormonal therapy (with the exception of hormones for thyroid conditions or estrogen replacement therapy), and other investigational agents are not allowed during study drug treatment. Treatment with supportive medications for MF such as interferon, erythropoietin, danazol, and steroids, is not permitted during study drug treatment. Steroid therapy for MF or for anti-neoplastic intent will not be allowed within 7 days prior to the first dose of study treatment or during study drug treatment. If medically indicated, allowed steroid therapy includes inhalational steroids for the treatment of asthma or chronic obstructive pulmonary disease, topical steroids, and steroids for prevention and/or treatment of transfusion related reactions. Steroids for any other indications should be limited to lower dose and/or short duration.

Biologics for MF will not be allowed within 30 days prior to the first dose of study drug and during navitoclax/placebo or ruxolitinib administration.

Medication that interferes with coagulation or platelet function (e.g., warfarin, apixaban, clopidogrel, tirofiban, disulfiram [potential prolongation of PT]), except for low dose aspirin (up to 100 mg daily) and LMWH, are not allowed during study drug treatment. Dose adjustments for LMWH should be made based on the subject's platelet counts and the local label of the agent being used concomitantly.

Hydroxyurea or other medications used for cytoreduction should be discontinued 7 days prior to first dose of study drug and are not allowed during study drug treatment.

Janus kinase inhibitors for the treatment of inflammatory diseases are not permitted during study drug treatment.

Treatment with NSAIDs for limited duration is permitted during study treatment if platelet counts $>100 \times 10^9/L$.

Selective serotonin re-uptake inhibitors and serotonin and norepinephrine reuptake inhibitors (SSRIs and SNRIs; e.g., citalopram, escitalopram, fluoxetine, paroxetine, sertraline, duloxetine, venlafaxine) are cautionary as they may increase the risk of bleeding events.

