5.5 Subject Discontinuation from Study Drug Treatment and Discontinuation of Study

Treatment with study drug may continue until end of clinical benefit or occurrence of unacceptable toxicity or discontinuation from study. A subject may voluntarily withdraw or be withdrawn from study drug treatment at any time for reasons including, but not limited to, the following:

- The subject is no longer deriving clinical benefit from study drug treatment, has disease progression, or the investigator believes it is in the best interests of the subject.
- The subject requires alternative therapy for treatment of MF.
- Clinically significant abnormal laboratory results or AEs, which rule out continuation of the study drug, as determined by the investigator or the AbbVie TA MD.
- Eligibility criteria violation was noted after the subject started study drug and continuation of the study drug would place the subject at risk.

- Introduction of prohibited medications and continuation of the study drug would place the subject at risk.
- The subject becomes pregnant while on study drug, or begins or intends breastfeeding.
- Significant subject noncompliance with study drug administration, study procedures, or study requirements, which would put the subject at risk for continued participation in the trial.
- The subject withdraws consent to receiving study drug treatment.
- Any other medical reason that AbbVie or the investigator deems appropriate.
- If the study treatment is unblinded by the investigator, that subject would need to be discontinued from study treatment and post-treatment or survival follow-up would commence.

Withdrawal from study (including all follow-up) will occur under the following circumstances:

- Withdrawal of consent for follow-up (this request must be documented in the subject's medical records and signed by the investigator)
- Lost to follow-up
- Death of subject
- Study termination by Sponsor.

Discussion with the TA MD/SD is recommended prior to discontinuation of a subject from study treatment for any reason other than described above to ensure all acceptable mitigation steps have been evaluated.

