8.4.1.4 Anemia Response

Definition of Baseline Transfusion Dependence

Baseline transfusion dependence (TD) is defined as transfusion of at least 6 units of packed red blood cells (PRBC) within 12 weeks on or prior to the date of the first dose of study drug (or randomization for untreated subjects). In addition, the most recent transfusion episode must have occurred within 4 weeks on or prior to the date of the first dose of study drug (or randomization for untreated subjects). Subjects with baseline hemoglobin level of < 10 g/dL who do not meet the criteria for baseline transfusion dependence are considered baseline transfusion independent (TI).

Definition of Baseline Hemoglobin

For subjects who receive PRBC transfusion within 4 weeks on or prior to the date of the first dose of study drug (or randomization for untreated subjects), the baseline hemoglobin value is defined as the minimum of the hemoglobin value collected prior to the transfusion, if available, and the last non-missing hemoglobin value on or prior to the date of the first dose of study drug (or randomization for untreated subjects).

For subjects who do not receive PRBC transfusion within 4 weeks on or prior to the date of the first dose of study drug (or randomization for untreated subjects), the baseline hemoglobin value is defined as the last non-missing hemoglobin value on or prior to the date of the first dose of study drug (or randomization for untreated subjects).

Definition of Anemia Response

For subjects who are baseline transfusion independent and whose baseline hemoglobin is < 10 g/dL, anemia response is defined as ≥ 2 g/dL increase in hemoglobin from baseline without receiving any PRBC transfusion within 2 weeks or erythropoietin supplements within 4 weeks. Hemoglobin values after the last dose + 30 days, confirmed disease progression or start of post-study treatment will not be considered in the analysis of anemia response.

For subjects who are baseline transfusion dependent, anemia response is defined as a period of at least 12 consecutive weeks without PRBC transfusion after the first dose of study drug until the last dose + 30 days, start of post-study treatment, confirmed disease progression or death, which occurs earlier.

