Subjects who do not receive any study drug will be treated as non-responders. Subjects who are baseline transfusion independent and whose baseline hemoglobin is ≥ 10 g/dL will not be included in the analysis since these subjects are not applicable to the evaluation of anemia response.

Anemia response rate is defined as the proportion of subjects who achieve anemia response and will be analyzed using the statistical method described for binary variables in Section 8.1. The main analysis of anemia response will include both TD and TI subjects, with separate summaries provided for TD and TI subjects.

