Appendix A. Protocol Deviations

The number and percentage of subjects who reported at least one of the following protocol deviation categories will be provided.

- Subject entered into the study even though s/he did not satisfy entry criteria.
- Subject developed withdrawal criteria during the study and was not withdrawn.
- Subject received wrong treatment or incorrect dose of study.
- Subject took prohibited concomitant medication.

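### The anemia response definition excludes erythropoietin for transfusion-independent responders but not for transfusion-dependent ones, although both feed one ranked test (minor)

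*SAP*

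**What the plan says.** SAP 8.4.1.4 defines anemia response separately for two groups. TI subjects with baseline hemoglobin below 10 g/dL must gain at least 2 g/dL "without receiving any PRBC transfusion within 2 weeks or erythropoietin supplements within 4 weeks". For TD subjects, "anemia response is defined as a period of at least 12 consecutive weeks without PRBC transfusion after the first dose of study drug", in a window that runs "until the last dose + 30 days, start of post-study treatment, confirmed disease progression or death, which occurs earlier". The same section states: "The main analysis of anemia response will include both TD and TI subjects". Separate TD and TI summaries are also planned.

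SAP Table 1 places anemia response fourth in the fixed sequence at two-sided 0.05. (Protocol 7.6, which does not count the primary endpoint, lists it third among the key secondaries.) Fibrosis, OS, LFS, fatigue and physical functioning come after it.

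On co-medication, protocol 5.3 says: "Treatment with supportive medications for MF such as interferon, erythropoietin, danazol, and steroids, is not permitted during study drug treatment".

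**The concern.** Within one pooled comparison, the same exposure is treated in two ways. Recent erythropoietin disqualifies a TI subject's hemoglobin rise. A TD subject who goes 12 weeks without red cells while taking it is a responder as the rule is written. The SAP gives no reason for the difference. Its version history records for version 2.0 that erythropoietin was added to the anemia response definition, and draws no distinction between the groups.

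The endpoint is meant to reflect the effect of adding navitoclax. A TD response obtained on erythropoietin does not do so cleanly, and if such use differed between arms it would distort a test on which five later claims depend.

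**Working it through.** The plan gives no sample size, power or expected rate for anemia response, so there is no stated figure to reproduce. The check is mainly a reading of the rules, followed by an illustration of size.

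**1. The two rules side by side (SAP 8.4.1.4)**

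| Element | TI, Hb < 10 g/dL | TD |
|---|---|---|
| Criterion | Hb up by ≥ 2 g/dL | ≥ 12 consecutive weeks free of PRBC |
| Erythropoietin | must be absent for 4 weeks | no condition |
| Danazol, steroids | no condition | no condition |
| Data stop at | last dose + 30 days, confirmed progression, post-study treatment | the same, or death |

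The asymmetry concerns erythropoietin only.

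**2. Does another rule catch the TD case?**

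- Protocol 5.3 prohibits the drug on treatment but does not say how the endpoint is scored after a breach.
- Protocol 5.5 lists, among reasons for which a subject may be withdrawn from study drug, "Introduction of prohibited medications and continuation of the study drug would place the subject at risk". This is permissive and conditional.
- SAP Appendix A counts subjects under "Subject took prohibited concomitant medication". That is a tabulation and does not change responder status.
- SAP 8.1 and 8.2 (general conventions and missing data) have no step for prohibited medication.
- The TD window does not close when such a drug is started on treatment. SAP 8.4.1.4 does not say what counts as post-study treatment, so it is unclear whether erythropoietin begun after the last dose would close it.

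Nothing therefore turns the case into a non-response.

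**3. How much can the 30-day tail contribute?** Twelve weeks is 84 days. At most 30 of them can fall after the last dose, so at least 84 − 30 = 54 days must fall while the subject is still on study drug. Tail use can complete a qualifying period but cannot supply all of it.

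**4. Size per subject.** About 230 subjects at 1:1 gives 115 per arm. TI subjects with hemoglobin of at least 10 g/dL are left out of the analysis. The documents do not give the evaluable share. Assuming 40% to 60%:

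- n = 0.40 × 115 = 46 to 0.60 × 115 = 69 per arm
- shift in that arm's rate = k/n for k affected subjects
- k = 1: 1/69 = 1.4 points to 1/46 = 2.2 points
- k = 3: 3/69 = 4.3 points to 3/46 = 6.5 points

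**5. Effect on the test, as an illustration.** Assume a true rate of 25% in both arms, with one arm inflated by δ and the other not at all. Use an unstratified normal approximation in place of the stratified CMH test:

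P(reject) = Φ[(δ − 1.96·se0)/se1] + Φ[(−δ − 1.96·se0)/se1]

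Here se0 uses the pooled rate and se1 the separate rates. For n = 50 and δ = 0.05, the pooled rate is 0.275, se0 = √(0.275 × 0.725 × 2/50) = 0.0893 and se1 = √((0.25 × 0.75 + 0.30 × 0.70)/50) = 0.0892. The result is 8.6%.

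| δ | n = 50 | n = 70 |
|---|---|---|
| 0 | 5.0% | 5.0% |
| 2 points | 5.6% | 5.8% |
| 5 points | 8.6% | 10.1% |
| 10 points | 19.2% | 25.1% |

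Five points corresponds to 2.5 subjects at n = 50 and 3.5 at n = 70, all in one arm.

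**The case against.** The strongest reply is that the case requires a protocol breach. Erythropoietin is barred on treatment, protocol 5.11 allows no intentional deviations except to avert an immediate hazard, and protocol 5.5 also lists a need for alternative MF therapy as a reason to stop study drug. An affected subject must be TD at baseline, take the drug anyway or in the tail, and become transfusion-free for 12 weeks because of it. The trial is double-blind, and equal use would not create the between-arm distortion. Separate TD and TI summaries, tabulated concomitant medication and the deviation count could expose an artefact. All of this stands and limits the weight of the point. None of it changes how the subject is scored.

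A reader might infer from the TI condition that the sponsor expects erythropoietin use on study. The documents do not support that. Eligibility criterion 4 asks for only 14 days free of growth factors before Day 1. If that covers erythropoietin, a 4-week condition protects an early hemoglobin value from pre-study carry-over, to which a single reading is more exposed than a 12-week period. TI values also count for 30 days after the last dose, when the on-treatment ban no longer applies. The endpoint is labelled as following IWG criteria, and the wording may simply come from that source, which is not available here.

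A reader might also see the silence on danazol and steroids as the same error. It is not: neither rule excludes them, so there is no inconsistency to correct. Protocol 5.3 also permits some steroid use, for example "Steroids for any other indications should be limited to lower dose and/or short duration". Adding these drugs to the main definition would be an extension and might depart from the IWG criteria.

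**Conclusion.** The gap in the text is real: as written, SAP 8.4.1.4 credits a TD response obtained on erythropoietin and refuses the corresponding TI response, within one ranked test. Severity is minor. The figure of 1.4 to 2.2 points per affected subject rests entirely on the assumed 46 to 69 evaluable subjects per arm. The false-positive figures rest further on a 25% rate in both arms and on use confined to one arm.

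It is tempting to conclude that the test is biased towards navitoclax, because anemia is a known reaction to the combination and that arm might receive more erythropoietin. The documents do not support that conclusion. They give no number of TD subjects, no expected use and no between-arm difference, so neither the size nor the direction of a bias can be derived.

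**What to change.** In the TD part of SAP 8.4.1.4, require that the qualifying 12-week PRBC-free period has no erythropoietin during it or in the 4 weeks before it starts, in line with the TI rule. This also removes the doubt over whether erythropoietin begun after the last dose closes the window. Finalise the change before unblinding. If that is no longer possible, leave the main definition as it is and report a sensitivity analysis that counts such TD subjects as non-responders.

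For danazol and steroids given for MF, add a sensitivity analysis that counts TI and TD users as non-responders, and leave the main definition unchanged.

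The cost is SAP wording and some programming. Protocol 5.4 already records medication from consent to 30 days after the last dose, which matches the end of the TD window. For a period that begins in the first 4 weeks of treatment, the look-back reaches before the first dose, so check that the prior-medication data cover it. The downside is that a few TD responders may be lost in either arm.

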8.4.1.5 Change in Physical Functioning at Week 24 from Baseline

Physical functioning will be assessed using the physical functioning domain of EORTC QLQ-C30⁵. Scores will be computed according to the EORTC QLQ-C30 scoring manual. Change in scores from baseline at Week 24 will be compared between the treatment arms using the linear mixed effects model described in Section 8.1. The tipping point analysis described in Section 8.2 will be performed as sensitivity analyses.

8.4.1.6 Reduction in Grade of Bone Marrow Fibrosis from Baseline

Grade of bone marrow fibrosis will be measured by the European consensus grading system⁶ and assessed centrally. The proportion of subjects who achieve a reduction of at least 1 grade in bone marrow fibrosis from baseline will be analyzed using the statistical method described for binary variables in Section 8.1. Data after subjects have confirmed disease progression or started post-study treatment will be excluded from the analysis.

Subjects without any post-baseline grade of bone marrow fibrosis measurement will be treated as non-responders. Subjects who do not receive any study drug will be treated as non-responders. Subjects without baseline bone marrow fibrosis assessment will be treated as non-responders.

The analysis of reduction in grade of bone marrow fibrosis will be performed on subjects who have a bone marrow fibrosis grade determined at baseline and have at least one post-baseline assessment.

Time to first reduction in grade of bone marrow fibrosis from baseline will be descriptively summarized for each treatment arm. Reduction in grade of bone marrow fibrosis at Week 24 will be descriptively summarized.

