7.2 Definition for Analysis Populations

The intent-to treat (ITT) population includes all randomized subjects in the study. Data from the ITT population will be analyzed by the treatment arm (Arm A: navitoclax + ruxolitinib, and Arm B: placebo + ruxolitinib) assigned at the time of randomization, regardless of the study drug treatment actually received. The ITT population will be used for analyses of all efficacy and baseline characteristics.

The safety population consists of all subjects who received at least 1 dose of study drug. The safety population will be used for all safety analyses.

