Anemia response rate is defined as the proportion of subjects who achieve anemia response at any time during the study.

Overall survival is defined as time from randomization to death from any cause.

Leukemia-free survival is defined as time from randomization to leukemic transformation ($\geq 20\%$ blasts) by bone marrow blasts or peripheral blood blasts per IWG criteria, or death from any cause, whichever occurs earlier.

Rate of reduction in grade of bone marrow fibrosis is defined as the proportion of subjects who achieve reduction of at least 1 grade in bone marrow fibrosis measured by the European consensus grading system.

Unless otherwise specified, all response rate secondary endpoints will be analyzed using the stratified CMH test. The point estimate and 95% CIs based on the exact binomial distribution will be presented for each treatment arm. Unless otherwise specified, subjects with missing data for a visit will be treated as non-responders for that visit.

Unless otherwise specified, all time to event secondary endpoints will be analyzed by using stratified log-rank test. Subjects who do not experience the event of interest will be censored at the last adequate assessment. The hazard ratio (HR) for treatment effect and the corresponding 95% CI will be estimated using stratified Cox proportional hazards model. In addition, survivorship functions will be estimated by using Kaplan-Meier product-limit method. Estimated survival curves will be presented.

Unless otherwise specified, all continuous patient-reported outcome endpoints will be analyzed using the linear mixed effects model. Subjects with missing data will be handled by the missing at random assumption within the framework of the linear mixed effects model.

Statistical analyses of secondary endpoints will be described in detail in the SAP.

Additional Efficacy Analyses

Details of additional efficacy analyses will be provided in the SAP. Additional supportive efficacy statistical analyses may be performed if deemed necessary and helpful in understanding the drug effect.

Subgroup Analysis for Efficacy

Supportive subgroup analyses, such as platelet count and DIPSS+, will be performed for the primary endpoint. Details of subgroup analyses will be provided in the SAP.

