4.0 Analysis Populations

The following population sets will be used for the analyses.

The Intent-to-Treat (ITT) Population includes all randomized subjects. Unless otherwise specified, the ITT Population will be used for all efficacy analyses. Subjects will be included in the analysis according to the treatment arms that they are randomized to.

The TSS Sensitivity Analysis Population includes all randomized subjects who meet the following criteria:

- subjects with baseline TSS score ≥ 12 ; or
- subjects with at least 2 symptoms with a baseline symptom score ≥ 3 .

The Safety Analysis Set consists of all subjects who received at least 1 dose of any component of the study drug. Subjects will be included in the analysis according to the study drug that they actually received.

The pharmacokinetic (PK) analysis population consists of all subjects who received at least 1 dose of navitoclax. The PK analysis population will be used for all PK analyses.

The study drug is defined as any component of navitoclax + ruxolitinib for subjects in Arm A and any component of placebo + ruxolitinib for subjects in Arm B.

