TSS analyses will be performed on the ITT population. Sensitivity analyses will be performed using the TSS Sensitivity Analysis Population described in Section 4.0.

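### SAP 8.4.1.6 gives two incompatible denominators for the alpha-controlled bone marrow fibrosis test, and that test gates OS, LFS, fatigue and physical functioning

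*SAP*

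**What the plan says.** SAP 8.4.1.6 defines response as a drop of at least one fibrosis grade, assessed centrally, and sends the comparison to the stratified CMH test of SAP 8.1. It then sets two rules.

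- **Missing counts as failure.** "Subjects without any post-baseline grade of bone marrow fibrosis measurement will be treated as non-responders", and "Subjects without baseline bone marrow fibrosis assessment will be treated as non-responders". Untreated subjects are also non-responders.
- **Missing is excluded.** The next paragraph says the analysis "will be performed on subjects who have a bone marrow fibrosis grade determined at baseline and have at least one post-baseline assessment".

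The general rules are these.

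- Protocol 7.2: "The ITT population will be used for analyses of all efficacy and baseline characteristics". This carries no exception.
- Protocol 7.3: "Unless otherwise specified, subjects with missing data for a visit will be treated as non-responders for that visit".
- SAP 4.0: "Unless otherwise specified, the ITT Population will be used for all efficacy analyses". SAP 8.2 has the same non-responder default for binary variables, also open to exceptions.

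SAP 12.0, Table 1, places fibrosis fifth, tested once at the Week 48 analysis at two-sided 0.05. OS, LFS, fatigue and physical functioning follow. Protocol 7.6 gives the same order.

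**The concern.** A non-responder is in the denominator; an excluded subject is not. One test cannot follow both rules, and the SAP does not say which one carries the alpha.

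The restricted set also depends on something that happens after randomisation, namely having a post-baseline biopsy. If biopsy availability differs by arm and is related to response, the comparison is no longer protected by randomisation.

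Because fibrosis is a gate, the choice of denominator can decide whether a survival claim is reachable. The test runs at Week 48, after the primary analysis, so an unresolved choice could end up being made once unblinded results are known.

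**Working it through.** **1. Do the rules conflict?** Take a randomised, treated subject with no baseline grade. The first rule counts the subject as a failure; the second removes the subject. The same holds for a subject with a baseline grade and no later biopsy. The conflict is in the text and needs no arithmetic.

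**2. Do other parts of the plan settle it?** Protocol 7.2 points to ITT without qualification. The defaults in protocol 7.3, SAP 4.0 and SAP 8.2 give way to endpoint-specific text, and the restricting sentence is endpoint-specific. Elsewhere the SAP is explicit:

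- For TSS it names ITT and then adds "Sensitivity analyses will be performed using the TSS Sensitivity Analysis Population described in Section 4.0".
- For anemia response it names a main analysis and gives a baseline-defined reason for leaving out some subjects, who "will not be included in the analysis since these subjects are not applicable to the evaluation of anemia response".
- For SVR35 (8.4.1.2) and palpable spleen (8.5.1) it has parallel non-responder rules and no restricting sentence.

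The fibrosis restriction has neither a label nor a reason.

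**3. Can the choice change the result?** The documents state no power, control rate or missing-biopsy rate for this test, so there is no planned figure to reproduce. The only inputs they give are about 230 subjects randomised 1:1 (115 per arm) and two-sided 0.05. All responder and availability counts below are assumptions.

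Formula (unstratified, because stratum data are not available): z = (x1/n1 − x2/n2) / √[p(1−p)(1/n1 + 1/n2)], with p = (x1+x2)/(n1+n2).

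Worked for case 1:

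- All randomised: 34/115 − 24/115 = 0.0870; p = 58/230 = 0.2522; SE = 0.0573; z = 1.52; p-value 0.129.
- Restricted: 34/86 − 24/98 = 0.1505; p = 58/184 = 0.3152; SE = 0.0686; z = 2.19; p-value 0.028.

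| Case (Arm A v Arm B) | Restricted | p | All randomised | p |
|---|---|---|---|---|
| 1. Fewer graded in A | 34/86 v 24/98 | 0.028 | 34/115 v 24/115 | 0.129 |
| 2. Fewer graded in B | 31/98 v 18/86 | 0.101 | 31/115 v 18/115 | 0.036 |
| 3. Equal, 80% graded | 38/92 v 25/92 | 0.043 | 38/115 v 25/115 | 0.055 |

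The estimated effect favours Arm A in every cell; only significance changes.

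The next table holds responders at 35 v 23, for which the all-randomised p is always 0.068.

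| Missing, A v B | Restricted p |
|---|---|
| 10% v 10% | 0.063 |
| 20% v 20% | 0.057 |
| 30% v 30% | 0.049 |
| 30% v 20% | 0.011 |
| 20% v 30% | 0.180 |

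**4. Type I error.** Simulated trials of 115 per arm with a true rate of 25% in both arms, tested with a single-stratum CMH at 0.05:

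| Graded, A v B | Who is missing | Restricted | All randomised |
|---|---|---|---|
| 75% v 85% | Only non-responders | about 0.09 | about 0.05 |
| 75% v 85% | Unrelated to response | about 0.05 | about 0.076 |
| 85% v 90% | Only non-responders | about 0.057 | about 0.05 |
| 85% v 90% | Unrelated to response | about 0.05 | about 0.057 |
| 80% v 80% | Either | about 0.05 | about 0.05 |

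**5. How often would the versions disagree?** With assumed true rates of 35% v 22%, they differ on significance in 18–25% of simulated trials with a 10-point availability gap, in 9–11% at an equal 80%, and in about 7% at an equal 90%.

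**The case against.** - **The protocol already points one way.** Protocol 7.2 is unconditional, and the SAP defaults agree with it, so a careful reader could infer ITT. This stands, and it is the best ground for the fix. It does not repair the SAP, whose specific sentence speaks of the analysis itself and not of an additional one.
- **The wording is looser than it looks.** The restriction asks for a post-baseline assessment, not a post-baseline grade. Read literally, a subject whose later biopsy could not be graded stays in and counts as a failure, so the post-baseline rule is not entirely emptied. That is fair. The missing-baseline rule is still emptied, and subjects with no later biopsy are still dropped.
- **The numbers are chosen.** The flips sit near 0.05, and nothing in the documents points to a 10-point gap or to 20% missing. Protocol Appendix D schedules fibrosis biopsies at treatment completion and post-treatment visits, so many early discontinuers can be graded. This also stands: the tables show what is possible, not what is expected.
- **The gate matters only if ranks 1 to 4 succeed** (SVR35W24, TSS, SVR35, anemia response). True, and the primary endpoint is unaffected.
- **Neither denominator is best under every mechanism.** Step 4 shows this. It is a reason to keep both analyses, not to leave the confirmatory one unnamed.

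**Conclusion.** The concern holds. SAP 8.4.1.6 prescribes two different denominators for one confirmatory test and ranks neither. The conclusion rests on the text alone. The direction and size of the effect are unknown, because no biopsy-availability or control-arm fibrosis rate is given. Under the assumptions above, the choice can move the p-value across 0.05 in either direction. With equal missingness of 20% or less and 35 v 23 responders, it moves the p-value by only about 0.01. Even so, the choice must be fixed in advance: the test gates two survival endpoints and two patient-reported endpoints, and it is run after the primary results are available.

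**What to change.** In SAP 8.4.1.6:

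1. State that the confirmatory Week 48 stratified CMH test uses all randomised subjects, with untreated subjects and those lacking a usable baseline or post-baseline grade counted as non-responders. This follows protocol 7.2.
2. Relabel the restricted analysis as a sensitivity analysis with no alpha, in the way the SAP already does for TSS. State whether it requires a post-baseline grade or only an assessment.
3. Report the number without a usable fibrosis grade, by arm and reason (for example death, withdrawal, refused biopsy, or first biopsy after progression or new therapy).

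Make the change before the primary analysis is run. The cost is two or three sentences and one table row, with no new data and no protocol amendment. Reported rates will be lower; in case 1, Arm A shows 34/115 = 29.6% instead of 34/86 = 39.5%. If missingness is unequal but unrelated to response, the ITT version penalises the arm with more missing grades, which is why the restricted analysis should be kept as support.
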